10.2 Serious Adverse Events

The Site Investigator is initially responsible for classifying AEs as serious or non-serious. An AE is considered serious if it meets one or more of the following criteria:

- Results in death
- Is life-threatening (i.e., a subject is at immediate risk of death at the time the AE occurs, not an event where occurrence in a more serious form might have caused death)
- Requires inpatient hospitalization or prolongation of existing hospitalization
 - Hospitalization for an elective procedure (including elective PEG tube, g-tube, feeding tube placement) or a routinely scheduled treatment is not an SAE by this criterion because an elective or scheduled "procedure" or a "treatment" is not an untoward medical occurrence.

- Results in persistent or significant disability/incapacity
 - This serious criterion applies if the “disability” caused by the reported AE results in a substantial disruption of the subject’s ability to carry out normal life function.
- Results in a congenital anomaly / birth defect
- Necessitates medical or surgical intervention to preclude permanent impairment of a body function or permanent damage to a body structure
- Is another important medical event
 - Important medical events that may not result in death, are not life-threatening, or do not require hospitalization may also be considered SAEs when, based upon appropriate medical judgment, may jeopardize the subject and may require medical or surgical intervention to prevent one of the outcomes listed in this definition. Examples of such medical events include blood dyscrasias or convulsions that do not result in inpatient hospitalization, or the development of drug dependency or drug abuse.

An inpatient hospital admission in the absence of a precipitating, treatment-emergent, clinical adverse event may meet criteria for “seriousness” but is not an *adverse* experience, and will therefore not be considered an SAE. An example of this would include a social admission (subject admitted for other reasons than medical, e.g., lives far from the hospital, has no place to sleep).

A serious, suspected adverse drug reaction is an SAE that, in the opinion of the Site Investigator or Sponsor, suggests a reasonable possibility that the investigational product caused the event.

Serious adverse events (SAEs) will be collected and reported on subjects who receive investigational treatment from signing of ICF through study Day 30. All SAEs must be reported within 24 hours of the site being notified of the event. All SAEs should be followed until resolution (or resolution with sequelae), but no longer than Day 90.

The Protocol PI will appoint an Independent Medical Monitor (IMM). Upon entry of an SAE by a clinical site, the NeuroNEXT Online Adverse Event Reporting System (AERS) will immediately notify the IMM. The IMM will review the SAE report to assess seriousness, expectedness and relatedness to study treatment, and may request further information if necessary. An unexpected SAE is any SAE for which the specificity or severity is not consistent with the current Investigators Brochure or package insert or described in the protocol. An unexpected, suspected adverse drug reaction is any unexpected SAE that, in the opinion of the IMM is at least possibly related to study treatment. Such SAEs (unexpected and at least possibly treatment-related) require expedited reporting to the FDA. The DCC will prepare a MedWatch safety report for submission to the FDA. If warranted, the IMM will notify the DSMB chair.

10.3 Neuroworsening

For the purposes of this protocol, the incidence of “neuroworsening” is expected to be significant in this trial of acutely ill stroke patients. Per the protocol, neurological worsening is defined as a 4 or more point increase on the NIHSS, as compared to the most recent NIHSS, that lasts for more than 8 hours, is confirmed by a repeat NIHSS, follows administration of study drug, is resulting from edema, hemorrhage, hydrocephalus, and/or extending infarct, and is not felt to be attributable to non-neurological causes, such as iatrogenic sedation or medical co-morbidities. The cause of the neuroworsening will be captured as a serious adverse event, and must be declared by the site PI as hemorrhage, progressive cerebral edema, new infarct, or hydrocephalus. If occurring during the DLT reporting period, will be evaluated by the IMM as a potential DLT. For each case, sufficient imaging will be selected by the CSS Investigator, de-identified, and submitted to the IMM for review so that he can confirm the reason for neuroworsening. Refer to the ‘Imaging Plan’ for details. The Site Investigator will be asked to give primary and contributing causes of the worsening, and to gauge the depth of worsening by performing a NIHSS as close to the nadir as possible. The IMM will review all cases of neuroworsening, and will refer suspected cases of SICH to the SRC for adjudication. Refer to the ‘Safety Management Plan’ for further details.

10.4 Symptomatic Intracranial Hemorrhage (SICH)

All patients will have a follow-up CT scan at 24-36 hours following the tPA bolus, per local SOC and as deemed necessary by the investigator. If a CSS uses MRI as SOC at this time point, it is encouraged that the MRI protocol for this study be used. Symptomatic intracranial hemorrhage is defined as blood present on CT or

MRI brain images that is associated with clinical worsening that meets the definition of neuroworsening (4 or more point increase in NIHSS; see section 3.3.3) *and* in the opinion of the investigator represents a clinically significant change that can be attributed to the hemorrhage (Wahlgren et al, 2007). For each case, sufficient imaging will be selected by the CSS Investigator, de-identified and submitted to the IMM and SRC for review so that the SRC can adjudicate the possible DLT. Refer to the 'Imaging Plan' and 'Safety Management Plan' for further details.

10.5 Independent Medical Monitor

The PPI will appoint an Independent Medical Monitor (IMM). The IMM responsibilities will include independent review of safety data, including but not limited to review of all SAEs and DLTs in near real-time to help inform the CRM. At Day 8 for each enrolled subject, the IMM will also review a patient profile for each subject in order to thoroughly evaluate each subject for DLTs (including cases of neuroworsening). The patient profile for this Day 8 review will include a review of data from Days 1-7 for categories such as demographics, medical history and medications, vital signs, ECG, laboratory results, infusions, AEs, SAEs, site reported DLTs, neuroworsening, stroke scales, and protocol deviations. Should a DLT be reported or suspected, the IMM will notify the SRC which will be convened to review the AE(s). Any non-serious AEs that occur during the DLT period, but are not reported until after the Day 8 review will be evaluated in real-time by the IMM for safety, neuroworsening, and DLTs. Any non-serious AEs that occur after the DLT observation period can be reviewed on a quarterly basis or sooner at the discretion of the IMM.

The IMM will also assess 'key images' as part of the safety review of SICH (a DLT) and all cases of neuroworsening (an SAE). The IMM's assessment of each 'key image' will be captured in the database as part of the AE narrative for a given event. The objectives of the IMM review are:

- To confirm the presence of gross hemorrhage when an Investigator reports a DLT of SICH
- To confirm the reason for neuroworsening (hemorrhage, edema, extending infarct, or hydrocephalus) as reported by the Site Investigator

The IMM will also review all events that meet the regulatory definition of an SAE in real-time, upon notification via the NeuroNEXT Online Adverse Event Reporting System (AERS). In addition to performing real-time reviews of all SAEs (as described in section 10.2), the IMM will also receive aggregate, blinded reports of all AEs for review on a quarterly basis (or as requested). These aggregate reports will summarize all AEs by severity, attribution (expected or unexpected), and relationship to study drug procedures in a tabular form. The report will also provide summary information on all neuroworsening events, confirmed DLTs, and deaths. The IMM will be responsible for providing a written summary of this review to the DCC. Should any concerns arise due to observed trends, the IMM will send a written recommendation to the DCC requesting that the report be forwarded to Protocol PIs, the SRC, and/or the Data and Safety Monitoring Board (DSMB), as appropriate.

10.6 Safety Review Committee

An independent Safety Review Committee (SRC) will be formed and charged with reviewing and adjudicating DLTs in order to objectively inform the CRM. The SRC will be comprised of a committee chair, the IMM, and three qualified participants – as outlined in the 'Safety Review Committee Charter'. For every reported DLT, the SRC will review the event and make a final determination as to whether or not an incident should be classified as a DLT. The SRC's final adjudication (DLT = yes/no) will be recorded using the DLT Adjudication Form as part of the IMM Evaluation Module. Assignment of the dose for the following cohort will not occur until all four subjects in a cohort have completed the Day 8 assessment and all potential DLTs have been reviewed by the SRC. The SRC will be responsible for final determination of whether a particular AE will be classified as a DLT, but will not participate directly in dose selection. On a quarterly basis, the SRC will also review the same aggregate reports viewed by the IMM (see section 10.5).

If in the extraordinarily unlikely event the Central Reader identifies a new suspected DLT that was not previously recognized for that subject, the Central Reader will inform the PPI who will contact the DCC to initiate the AE/DLT review process so that the DLT can be adjudicated by the SRC.

10.7 Data and Safety Monitoring Board

The monitoring of subject safety and data quality will follow the NINDS Guidelines for Data and Safety Monitoring in Clinical Trials. A DSMB, appointed by NIH/NINDS, will meet at approximately six-month intervals (or as determined by the NINDS) to review partially unblinded study data provided by the study statistician. The

DSMB will periodically review and evaluate the accumulated data for participant safety, adverse events, study conduct, and study progress. The DSMB may suggest changes to the protocol or consent form to the Study Chair as a consequence of AEs. The DSMB may also make recommendations to NINDS concerning continuation, modification, or termination of the study. The frequency and format of DSMB meetings, reports, and guidelines for interim analysis will be agreed upon prior to study subject enrollment.

10.8 Safety Analyses

In addition to the determination of an MTD, additional safety assessments will involve a comparison of treatment-related AEs and SAEs across all 3K3A-APC treated subjects (regardless of dose) versus placebo. First, the percentage of subjects who experience any treatment-related AE or SAE in each group will be compared using a Fisher's exact test. If the null hypothesis is rejected, with a greater frequency observed in the 3K3A-APC group, we will conclude that 3K3A-APC was associated with a significantly greater frequency of treatment-related AEs. If the hypothesis is not rejected, we will conclude that the study does not provide sufficient evidence to conclude that 3K3A-APC was associated with a significantly greater frequency of treatment-related AEs. In addition to an overall comparison, this hypothesis will be repeated for the percentage of subjects having at least one treatment-related AE within each MedDRA system organ class (SOC). If there are significant differences between groups within any specific SOC, then additional tests will compare differences across groups for specific MedDRA preferred terms in order to further explore the cause of observed differences.

In addition to the comparison of percentages in the manner described above, the rates of treatment-related AEs in each group will be compared using the following Poisson regression model:

$$\log\left(\frac{Y_i}{T_i}\right) = \beta_0 + \beta_1 x_{1i} + \epsilon_i$$

where

- Y_i represents the number of treatment related SAEs experienced by the i^{th} subject.
- T_i represents the number of days between the date of randomization and the date of last follow-up for the i^{th} subject.
- $x_i = 1$ if i^{th} subject was randomized to one of the 3K3A-APC dose groups, and 0 if the subject was randomized to placebo group
- ϵ_i is random error for the i^{th} subject

To determine if the rate of treatment related SAEs differ across treatment group we will test the following hypothesis:

$$H_0: \beta_1 = 0 \text{ vs. } H_A: \beta_1 \neq 0$$

If the null hypothesis is rejected, the direction of β_1 will indicate the direction of the observed effect. Values of $\beta_1 > 0$ indicate an increased rate of treatment-related AEs associated with the 3K3A-APC group, while values of $\beta_1 < 0$ indicate a decreased rate of treatment-related AEs associated with the 3K3A-APC group.

Treatment-related SAEs will be analyzed in the same manner described above. Additional safety analyses will assess all treatment-emergent AEs, treatment-emergent SAEs, unanticipated SAEs, treatment-related & unanticipated SAEs, neuroworsening events, DLTs, and deaths in a similar manner. Finally, all safety analyses will be repeated for each pairwise comparison of subjects in each specific 3K3A-APC dose groups versus the placebo group.

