2.3.3 Recombinant Human APC (drotrecogin alfa [activated], Xigris[®])

Xigris[®] [drotrecogin alfa (activated)] (Eli Lilly and Company, Indianapolis, IN) is a recombinant wildtype APC having the same amino acid sequence as the naturally occurring APC. Xigris[®] was approved in the US in 2001 (and in the EU in 2002) for treatment of severe sepsis. Although Xigris is no longer marketed because of lack of efficacy in a large post-marketing trial in patients with severe sepsis, bleeding was a dose-limiting side effect³⁸.

In the 1690-subject placebo-controlled study that was the basis for approval, the Xigris[®] arm had a higher proportion of patients with treatment-emergent adverse events of bleeding than did the placebo arm at all levels of severity, i.e., mild: 10.5% versus 7.7%; moderate: 5.5% versus 1.8%; and severe: 2.8% versus 1.3%. Serious bleeding events (e.g., gastrointestinal, intrathoracic or intracranial) were associated with Xigris[®] (3.5% versus 2.0% in placebo, p = 0.06), occurring more commonly in patients with predisposing conditions for bleeding, such as gastrointestinal ulceration, traumatic injury of a blood vessel or vascular organ, low platelet count or markedly abnormal parameters of coagulation (PT or aPTT)³⁹. The FDA-approved labeling for Xigris[®] (2008) reported an approximately 1% risk of intracerebral hemorrhage in sepsis patients during continuous infusion. There were no statistically significant differences between the two treatment groups in the percentage of patients who experienced at least one serious adverse event during the study drug infusion period (6.8% of Xigris-treated patients versus 6.5% of placebo-treated patients) or during the 28-day study period (12.5% of Xigris-treated patients versus 12.1% of placebo-treated patients).

Xigris[®] was recently under study in a Phase 1/2, multi-center, dose escalation safety and feasibility trial for treatment of acute ischemic stroke [Activated Protein C in Acute Stroke Trial (APCAST)]⁴⁰, however the study was terminated prematurely due to insufficient recruitment. As of September 2013, study results were not publically available.

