2.5 Clinical Studies of 3K3A-APC

A Phase 1 study, ZZ-3K3A-001, was conducted in 64 healthy adult volunteers to characterize the safety and PK profile of single ascending and multiple ascending IV doses of 3K3A-APC. Intravenous administration of 3K3A-APC or matching placebo to cohorts of healthy adult volunteers at doses up to 720 μ g/kg single-dose and 540 μ g/kg multiple-dose (every 12 hours for 5 doses) did not result in any serious adverse events, severe adverse events or withdrawal from study due to an adverse event. After review of AEs (moderate headache, nausea and vomiting and mild vertigo) in 1 of the 2 subjects who received a single-dose of 720 μ g/kg of 3K3A-APC, the SRC recommended reducing the dose to 540 μ g/kg in subsequent subjects in the cohort. For that reason, 540 μ g/kg was the highest dose evaluated in the multiple-dose cohorts. In summary, the

evaluated safety measures indicate that 540 μ g/kg is tolerated in single and multiple dosing in healthy volunteers.

The most common adverse events reported were mild or moderate; headache, hypertension, nausea and vomiting were reported in 54%, 8%, 8% and 4% of the 3K3A-APC treated subjects (n=50) respectively. Rates for the same events in placebo subjects (n=14) were 7%, 21%, 7% and 0%, respectively.

The majority of the drug-related AEs were headache; of subjects who received active drug across the four highest doses, headache occurred at least once in 3/10 (30%) subjects receiving 180 μ g/kg, in 8/10 (80%) subjects receiving 360 μ g/kg, in 9/10 (90%) subjects receiving 540 μ g/kg and in 2/2 (100%) subjects receiving 720 μ g/kg. Headache was reported in 1/14 (7%) subjects who received placebo. These data indicate that headache is related to 3K3A-APC exposure and appears to increase in frequency with dose. In no patient did headache lead to interruption of IMP or require treatment other than acetaminophen pain reliever.

Hypertension was reported with the second highest frequency; ten AEs of hypertension assessed as being related to the treatment occurred during the study. Four (4) of these AEs occurred in placebo-treated subjects (21% of all placebo-treated subjects), and 6 of these AEs occurred in 3K3A-APC-treated subjects (8% of all actively treated subjects). No association of hypertension with 3K3A-APC could be ascribed.

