6. ANALYSIS POPULATIONS

Since the primary objective aims to estimate a maximum tolerated dose, no formal testing will be involved. All analyses to address the key secondary objectives will be conducted at the 0.05 significance level. The analysis population of interest will differ depending on the objectives of any particular analysis.

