9.2 Secondary Outcome (Bleed Rates)

We also assessed the power of the study to evaluate bleed rates between all treated subjects (collapsed across doses) versus placebo subjects. Previous experience (Derex et al, 2004; Kidwell et al, 2004; Fiehler et al, 2007; Cheng et al, 2013; Harada et al, 2013; Kimura et al, 2013; Shoamanesh et al, 2013) suggests that the MRI-detected bleed rate for tPA-treated subjects should be approximately 30%-40%. Furthermore, it is expected from pre-clinical studies that treatment with APC could lead to a rather dramatic decrease in bleed rates for 3K3A-APC treated subjects (Cheng et al, 2006; Wang et al, 2012; Wang et al, 2013). Pre-clinical data suggest that 3K3A-APC could reduce bleeding seen after IV tPA or after mechanical thrombectomy (Wang et al, 2012; Wang et al, 2013). Thus, it is expected that the study could observe a difference between the groups as substantial as a reduction from a 40% bleed rate among placebo subjects to a lack of observed bleeding in the treated group. However, to assess power over a range of conditions, we computed power for all combinations of the following conditions:

- Placebo group bleed rates of 20%, 30%, and 40%
- 3K3A-APC treated group bleed rates of 0.5%, 5%, and 10%
- Overall sample sizes of 48 (36 treated / 12 control) and 88 (66 treated / 22 control) – in order to assess power under the scenario where the trial proceeds to the end and under the scenario where the study stops early for lack of observing any toxicity at the highest dose

Table 6 provides a summary of these power calculations. In general, we find:

- *If the original assumptions are correct:* We would have very high power (>90%) in either scenario.
- *If the original assumption regarding the placebo rate is correct, but the treated rate is a bit higher:* We would have very good power (>85%) if the study proceeds to the end. We would have lower, but a still acceptable level of power (>64%) if the study stops due to a lack of observed toxicity after 12 cohorts.
- *If the original assumption regarding the treatment rate is correct, but the placebo rate is a bit lower:* We would have decent power (>66%) in either scenario, or very good power (>84%) in the scenario where the study proceeds to the end.
- *If both assumptions are wrong (placebo rate lower, treatment rate higher):* There is lower power overall, but still reasonable power in a number of settings (such as 30% placebo rate versus 10% treated rate).

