- Grade 5 – Death: The AE results in death

The relationship of the AE to the investigational product should be specified by the Site Investigator, using the following definitions:

- Definitely Related: The reaction follows a reasonable temporal sequence from administration of investigational product; Follows a known or expected response pattern to the investigational product; and is confirmed by improvement on stopping or reducing the dosage of the investigational product, and reappearance of the reaction on repeated exposure. (suspected ADR)
- Probably Related: The reaction follows a reasonably temporal sequence from administration of investigational product; Is confirmed by discontinuation of the investigational product or by re-challenge; and cannot be reasonably explained by the known characteristics of the subject's clinical state. (suspected ADR)
- Possibly Related: The reaction follows a reasonably temporal sequence from administration of the investigational product and follows a known response pattern to the suspected investigational product; Reaction could have been produced by the investigational product or could have been produced by the subject's clinical state or by other modes of therapy administered to the subject. (suspected ADR)
- Unlikely to be Related: The reaction has little or no temporal sequence from administration of the investigational product, and/or a more likely alternative etiology exists.
- Unrelated: Concomitant illness, accident, or event with no reasonable association with treatment.

For the purposes of this study, an AE is considered to be treatment-related if the attribution is possible, probable, or definite. All AEs should be followed until resolution or a new baseline is established, but no longer than study Day 90.

Headache has been identified as an AE that we would like to further characterize. Therefore, all headaches that start after signing of the ICF should be documented as AEs, and Investigators should also complete the Headache Record CRF. A new AE form, and new Headache Record should be completed for each new headache during the first seven days. Headaches that start prior to signing of the ICF, and do not worsen, should be reported only on the Medical History CRF and the Headache Record CRF should not be completed. If, however, a headache begins prior to consent and later worsens it should be reported as an AE and the Headache Record CRF should be completed.

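### Because SAP 10.8 tests preferred terms only after a significant organ-class test, headache can go without a formal comparison, and no planned comparison combines all bleeding AEs

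*SAP*

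**What the plan says.** SAP 10.8 first compares the percentage of subjects with any treatment-related AE, all 3K3A-APC versus placebo, by Fisher's exact test. Then "this hypothesis will be repeated for the percentage of subjects having at least one treatment-related AE within each MedDRA system organ class (SOC". The next step is conditional: "If there are significant differences between groups within any specific SOC, then additional tests will compare differences across groups for specific MedDRA preferred terms". The closing paragraph of SAP 10.8 carries the approach over to treatment-emergent AEs, among other event sets, and to each dose against placebo.

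Headache is singled out in SAP 10.1: "Headache has been identified as an AE that we would like to further characterize". It has its own case report form, but no section of the SAP specifies a headache analysis. Protocol 2.5 gives the reason for the interest. In Phase 1, "headache, hypertension, nausea and vomiting were reported in 54%, 8%, 8% and 4% of the 3K3A-APC treated subjects", against 7% headache on placebo (1 of 14), and headache rose in frequency with dose.

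For bleeding, Protocol 2.3.3 reports that wild-type APC was dose-limited by it, and lists several sites: "Serious bleeding events (e.g., gastrointestinal, intrathoracic or intracranial". Neither document defines a comparison of all bleeding AEs combined.

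Three planned items cover part of the ground:

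- SAP 10 tabulates every AE by body system, preferred term and dose, without any condition.
- SAP 10.8 compares DLTs between arms. The DLT definition in SAP 2 includes symptomatic intracranial hemorrhage and other treatment-related bleeding that is serious or needs transfusion.
- SAP 8.2 compares hemorrhage and microbleeds on the Day 30 MRI.

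**The concern.** A test on a whole organ class counts a subject once, whatever the event. If many subjects in both arms already have another event in the class, adding headache changes the class percentage much less than it changes the headache percentage. SAP 10.3 says that neuroworsening "is expected to be significant in this trial of acutely ill stroke patients", so a high background in the nervous-system class is plausible. A real headache difference could then miss the class-level threshold, and the headache test would not be run.

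Bleeding has a different difficulty. If bleeding events are classified by site, an excess spread over several sites may reach significance in no single class, and no test adds them together. What is at stake is the formal between-arm evidence on the AE that the plan wants to characterise and on the main known risk of the parent molecule.

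**Working it through.** **Inputs from the documents.** SAP 9.2 gives "Overall sample sizes of 48 (36 treated / 12 control) and 88 (66 treated / 22 control" as arm sizes. SAP 1 plans about 115 subjects, 88 of them in cohorts, so placebo could reach 22 + (115 − 88) = 49 beside 66 treated. Phase 1 headache rates are 54% and 7% (Protocol 2.5).

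**Assumptions.**

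- Significance level: SAP 6 says "All analyses to address the key secondary objectives will be conducted at the 0.05 significance level" and sets none for safety tests. I use two-sided 0.05.
- Other events in the headache class affect a share b of subjects, equal in both arms and independent of headache. The documents give no b, so I show a range.
- Headache shares a class with other nervous-system events, and bleeding falls in different classes by site. The documents do not state the MedDRA mapping. Protocol 2.3.3 shows only that several organs can bleed.
- Headache at 30% versus 7% is an assumed smaller effect. Phase 1 enrolled healthy volunteers.

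**Check on the plan's own figure.** No power is stated for any AE test. The nearest figure is in SAP Table 6: 40% versus 10% with 22 and 66 subjects, power 85%.

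- Pooled rate: (66 × 0.10 + 22 × 0.40)/88 = 0.175
- Null SE: √[0.175 × 0.825 × (1/66 + 1/22)] = 0.0935
- Alternative SE: √(0.09/66 + 0.24/22) = 0.1108
- Power: Φ[(0.30 − 1.96 × 0.0935)/0.1108] = Φ(1.05) = 85.4%, which agrees.

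**Headache.** The class rate is 1 − (1 − b)(1 − h), where h is the headache rate. At b = 40% and h = 54% versus 7% this is 1 − 0.60 × 0.46 = 72.4% versus 1 − 0.60 × 0.93 = 44.2%. A headache difference of 47 points has become a class difference of 28. Power is the exact sum of the two binomial probabilities over all tables that Fisher's test rejects.

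| Headache, drug vs placebo | Arms | Direct test | Class test significant at b = 20% | b = 40% | b = 60% |
|---|---|---|---|---|---|
| 54% vs 7% | 66/22 | >99% | 87% | 61% | 37% |
| 54% vs 7% | 66/49 | >99% | 98% | 84% | 57% |
| 30% vs 7% | 66/22 | 60% | 30% | 18% | 10% |
| 30% vs 7% | 66/49 | 88% | 48% | 27% | 16% |

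At b = 0 the class test and the direct test coincide and nothing is lost. At b = 10% and Phase 1 rates, the class test is significant 95% (66/22) or 99.7% (66/49) of the time. At b = 10% and 30% versus 7%, it is 41% or 67%.

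**Bleeding.** Take an assumed 30% versus 10% in total, split evenly over three classes with 10% background in each. One pooled test has about 43% (66/22) or 73% (66/49) power. The chance that any site-specific term test is reached and is significant is about 1% or 17%.

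Protocol 2.3.3 gives wild-type APC bleeding AE rates by severity. Summed, and taking each patient as counted once, they are 10.5 + 5.5 + 2.8 = 18.8% versus 7.7 + 1.8 + 1.3 = 10.8%. At those rates even the pooled test has only about 7% or 17% power.

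**The case against.** A reader might infer that the rule hides headache. It does not: rates by preferred term and dose appear in the unconditional tables of SAP 10, and wishing to characterise an event promises no hypothesis test. What can be lost is the formal comparison, not the data.

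A reader might also infer that bleeding is never pooled. That goes too far. SAP 10.1 merges the main intracranial bleeding terms into one, the DLT comparison takes in serious or transfused treatment-related bleeding at any site, the Day 30 MRI has its own test, and SAP 8.3 adds subarachnoid hemorrhage after thrombectomy and Day 7 hemorrhage as exploratory outcomes. Each is partial, however:

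- DLTs end 48 hours after the last dose, mix bleeding with coagulation, liver and other laboratory events, and exclude subarachnoid hemorrhage after thrombectomy.
- The MRI analysis covers only the brain and only subjects with a Day 30 scan (SAP 6.3).

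Nor do the documents support saying that the organ-class step usually blocks the headache test. At the Phase 1 rates, the class test is significant more than half the time in five of the six settings tabulated.

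The dilution argument is also weaker for treatment-related AEs, the first analysis in SAP 10.8. Stroke complications count there only if judged at least possibly related, and SAP 10.1 ties that grade to a known response pattern of the drug. The loss should be larger for treatment-emergent AEs.

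Finally, testing classes before terms is a recognised way to limit the number of tests. That supports keeping the step in general. It does not require applying it to two events that the documents themselves identify in advance.

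**Conclusion.** The point holds as an omission in the formal safety comparisons. Headache has no planned comparison outside the organ-class step, and no comparison combines all bleeding AEs, extracranial and non-serious ones included.

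For headache the size depends on a background rate that the documents do not give. The loss is nil if headache is alone in its class and small at Phase 1 rates with a background of 10% or less. It becomes substantial with a common background or a smaller effect: at 30% versus 7% and 20% background, the chance falls from 60% to 30% (66/22) or from 88% to 48% (66/49). Being significant at class level is only the first hurdle, so these are upper limits on formally detecting headache under the rule.

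For bleeding the gap is the missing composite. A single test of it would still have little power at modest differences. The results rest on the assumed class mappings, on independence of headache from other events, and on a 0.05 level for safety tests.

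**What to change.** In SAP 10.8, prespecify two comparisons that do not depend on the organ-class result:

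1. any headache AE;
2. any bleeding AE at any site, from a list of terms fixed before database lock.

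Make each for all treated versus placebo and for each dose versus placebo. Report risk differences with confidence intervals beside the Fisher p-value, and label both as exploratory without multiplicity adjustment. Keep the organ-class step for all other terms.

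The cost is SAP wording and a term list, since the AE data are already collected. The downside is more unadjusted tests: 2 events × (1 pooled + up to 4 doses) = up to 10, or 20 if given for both treatment-emergent and treatment-related events. Given the low power of the bleeding composite, its estimate and interval should carry more weight than its p-value.
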